7.2.2 Protocol Subcommittee

The subcommittee consists of a chair (who is an investigator from one of the clinical centers), investigators from one or more other clinical centers, BCC staff, nurse coordinators, outside consultants

(if appropriate), and the NICHD Network Project Scientist. The Protocol Subcommittee is responsible for the preparation and conduct of the study, and reporting the progress of the study to the Steering Committee.

7.2.3 Publications Committee

[figure not shown]
The Publications Committee is a standing committee of the Steering Committee. The functions of this committee are to develop publication policies and to review all manuscripts and abstracts prior to submission. The goals of this committee are fair and appropriate authorship credit and high quality publications.

7.2.4 Data and Safety Monitoring Committee

The Data and Safety Monitoring Committee (DSMC), a group of individuals not affiliated with any of the participating institutions, was established by the NICHD. Before the trial can begin, the protocol must be approved by the committee. During the conduct of the study, the committee is charged with monitoring the emerging results for efficacy and safety, in addition to center performance and protocol adherence. Recommendations by the committee can include protocol modification, early termination for efficacy, or for unexpected safety problems. Recommendations are made to the NICHD and disseminated to the Steering Committee.

8 Study Timetable

Figure 1. Timetable

8.1 Training and Certification

A preliminary training with the nurse coordinators was held on January 2016 and a final training was conducted for research staff in July 2016, in addition to CLEaR or Fetal Medicine Foundation certification of individual sonographers not previously certified. Physicians and staff at each study site will also have to undergo training in the appropriate techniques of pessary sizing and placement prior to receiving approval to begin enrollment. Each participating center must be certified to start the trial before recruitment at that center can begin. The certification requirements are designed to ensure that personnel involved in the trial are committed to the study and proficient in study procedures, and that the center has satisfied regulatory requirements. Each center is required to obtain IRB approval for the study before they are certified to begin the trial. The trial is expected to start in August/September 2016, if approved.

8.2 Recruitment and Data Collection Period

Approximately 160,000 women deliver at MFMU Network centers annually. It is conservatively hypothesized that that 1.5% of the women will have a short cervix ≤ 20 mm. In the MFMU SCAN trial of nulliparous singletons, 2 % of those screened had a cervical length ≤ 20 mm before 23 weeks. In an analysis of the MFMU Network Prediction Study, 2.2% of parous women with a low-risk history had cervical length ≤ 20 mm at 22-24 week ultrasound.³⁸ In Hassan et al., 2.3% of women had a cervical length between 10 and 20 mm.¹²

A survey of the MFMU Network sites in 2014 showed that in approximately 50% of the delivery population the cervix is not routinely measured, in 20% of the population universal routine transvaginal cervical length screening is conducted and in 30% the cervix is measured or evaluated by abdominal scan with reflexive transvaginal screening if it is short. If it is assumed that 80% of women receive an ultrasound at 16-23 weeks, and that there is a 20% detection rate for short cervix where cervical length is not measured routinely, 100% detection with routine transvaginal cervical length screening and a 90% rate when there is abdominal scan with reflexive transvaginal cervical length measurement, then with 160,000 deliveries per year approximately 1100 potentially eligible women would be available for recruitment annually.

Table 3. Calculation of Potential Number of Women with Short Cervix Detectable per Year

Approach (% detection)	Percent of Delivery Population	Short Cx (1.5%)	With Ultrasound (80%) at 15-23 wks	Detected
No Screening (detection rate 20%)	50	1200	960	192
Cervical Measurement (detection rate 100%)	20	480	384	384
Abdominal Measurement (detection rate 90%)	30	720	576	518
				1094

Assuming that only 75% of these women are accessible and eligible and that only 50% consent to the study, this would translate to an enrollment rate of 410 women per year, or 34 per month. Thus enrollment could be achieved within 30 months, even assuming a gradual start-up. If the percentage of women accessible and eligible cervix is only 50%, enrollment could still be achieved in just over 3 years.

8.3 Final Analysis

After a three-month period for completion of data entry for the trial and close-out of the delivery and primary outcome, the data set will be locked and available for the primary and other main analysis.

Appendix A Design Summary

A Randomized Trial of Pessary in Singleton Pregnancies with a Short Cervix

OBJECTIVE: To determine whether pessary reduces the risk of preterm birth in women with a singleton gestation and a short cervix.

ORGANIZATION

Clinical Centers: Magee, UAB, Ohio State, Utah, Brown, Columbia, Case Western, UT-Houston, UNC, Northwestern, UTMB-Galveston, UPenn
 Subcommittee: [name] (Chair)

DESIGN

Major Eligibility Criteria: ❖ Singleton gestation
 ❖ Gestational age 16⁰ to 23⁶ wks
 ❖ Cervical length ≤ 20.0 mm

Groups: ❖ Usual Care (may include vaginal progesterone)
 ❖ Arabin Pessary + Usual Care

Random Allocation: Standard urn design; 1:1 allocation

Level of Masking: Unmasked

Stratification: ❖ Clinical site

Sample Size: ❖ 850

Assumptions: ❖ Outcome event=delivery < 37⁰ weeks gestation or fetal loss
 ❖ Usual care group event rate =28%
 ❖ Pessary group event rate =18.67% (33.3% reduction)
 ❖ Type I error = 2.5% (two sided with one comparison)
 ❖ Power =90%

Interim Analysis: ❖ Lan-DeMets group sequential method

SCHEDULED EVALUATIONS / DATA COLLECTION

Pre-Randomization: ❖ Cervical length measurement by trained sonographer
 ❖ Pregnancy, exposure and medical history

Randomization: ❖ Vaginal sample, vaginal Gram stain and vaginal pH

Post-randomization: ❖ Phone call to assess patient symptoms and compliance within 7 days of randomization
 ❖ Every four weeks: study visit to assess symptoms and compliance
 ❖ Study visit between 24 and 32wks: vaginal sample, vaginal Gram stain and vaginal pH
 ❖ Digital exam to ensure appropriate pessary placement (pessary group)

Delivery: ❖ Patient questionnaire 8 weeks after randomization and again at 37 wks gestation.
 ❖ Pessary group: assessed for fit or replacement, as needed
 ❖ Delivery and neonatal data

MANAGEMENT PROTOCOL

Both Groups: ❖ Vaginal progesterone per usual care and rescue cerclage if needed

Pessary Group: ❖ Placement management from randomization to < 37 wks

OUTCOME MEASURES

Primary: ❖ Delivery or fetal loss prior to 37 wks

Secondary: ❖ Randomization to delivery interval
 ❖ Gestational age at delivery
 ❖ Neonatal morbidity and mortality
 ❖ Lower genital tract or urinary tract infection
 ❖ Physician interventions including bedrest, cerclage, labor inhibition therapy

TIMETABLE

Enrollment: ❖ September 2016 to October 2019
 Data Collection: ❖ September 2016 to October 2019
 Closeout/Analysis: ❖ October 2019 to September 2021

References

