5.2 Sample Size and Power

A one-third reduction in preterm birth < 37 weeks was selected as being clinically meaningful. If it is conservatively assumed that the rate of preterm birth < 37 weeks in the progesterone arm is between 28% and 35%, then a sample of 850 women is sufficient to detect a 33% reduction in preterm birth at 90% power. In addition this sample size yields more than 80% power to detect a 30% reduction, assuming a type 1 error of 5% 2-sided.

Table 2. Sample Size for Various Outcome Rates and Effect Sizes

PTB rate in Usual care arm (%)	Total sample size for 30% reduction	Total sample size for 33.3% reduction
Power=80% ($\alpha=0.05$; $\beta=0.2$)		
28	810	640
30	740	590
32	680	540
35	600	480
Power=90% ($\alpha=0.05$; $\beta=0.1$)		
28	1080	850
30	990	790
32	900	720
35	800	640

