5.4 Interim Analysis

The DSMC meets in person at least once per year and more often if recommended by the committee. Before each of the annual meetings, a formal detailed report will be written by the Biostatistical Coordinating Center (BCC) which presents all baseline variables, protocol adherence, side effects, all adverse events reported, as well as center performance in terms of recruitment, data quality, loss to follow-up and protocol violations.

Once sufficient patients have been accrued into the trial, the report will also include a formal interim analysis evaluating the primary outcome by treatment group. For this evaluation, a cohort of patients is chosen consisting of all patients randomized before a certain date so that the analysis cohort does not depend on gestational age at delivery.

The main statistical issue relevant to interim analysis is the problem of performing multiple tests of significance on accumulating data. For this trial, the group sequential method of Lan and DeMets will be used to characterize the rate at which the type I error is spent.³⁴ This method is flexible with regard to the timing of the interim analyses. It is expected that an interim analysis will be conducted at approximately 50% of the final sample size of 850.

Asymmetric stopping boundaries will be used for the Lan-DeMets procedure. The upper boundary which describes the stopping rule for benefit will be based on 1-sided type I error of .025 and the Lan-DeMets generalization of the O'Brien-Fleming boundary. The lower boundary will be based on a less stringent stopping rule: 1-sided type I error of .05 and the Lan-DeMets generalization of the Pocock type boundary.

It is often useful to calculate conditional power given the observed data to date, and conditional on the future data showing the originally assumed design effect. If this conditional power is low (under 10 percent) the DSMC may consider termination for futility if the accrual rate is slow with confidence that the Type II error is not greatly inflated.³⁵

It is recognized that any decision to terminate the study would not be reached solely on statistical grounds but on a number of complex clinical and statistical considerations.

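### Appendix A gives the type I error as 2.5% two-sided; Section 5.2, Table 2 and the sample size of 850 all rest on 5% two-sided

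*Combined protocol and SAP*

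**What the plan says.** **Appendix A, Assumptions.** The list gives a usual-care event rate of 28%, "Pessary group event rate =18.67% (33.3% reduction"), 90% power and a sample size of 850. For the error rate it gives "Type I error = 2.5% (two sided with one comparison").

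**Section 5.2.** For usual-care rates of 28% to 35%, "a sample of 850 women is sufficient to detect a 33% reduction in preterm birth at 90% power". The section also claims more than 80% power for a 30% reduction, "assuming a type 1 error of 5% 2-sided". Both power blocks of Table 2 are headed with an alpha of 0.05, and the 850 is its cell for 28%, a 33.3% reduction and 90% power.

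**Section 5.4.** For the interim analysis, "the stopping rule for benefit will be based on 1-sided type I error of .025", with O'Brien-Fleming-type spending. The other side has a separate rule: "The lower boundary will be based on a less stringent stopping rule: 1-sided type I error of .05", with Pocock-type spending.

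**Section 5.5.** The primary analysis compares two binomial proportions and reports a relative risk with a confidence interval. No significance level or confidence level is stated.

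**The concern.** Two different two-sided error rates are attached to one design: the same rates, effect, power and sample size. Both are current text, and nothing in the document says that the body prevails over the appendix.

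No multiplicity adjustment explains the lower figure. There are two arms and one primary outcome, and the Appendix A line itself refers to a single comparison.

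Two things are at stake. If 2.5% two-sided were intended, 850 women would be too few for the stated power. If 5% were intended, the design summary misstates the level at which the primary result will be judged. Because Section 5.5 is silent, a reader must take the level from Section 5.2 or from Appendix A. The trial is unmasked, which is a further reason to settle this in writing before results by arm are known.

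**Working it through.** **Inputs.** p1 = 0.28 and a one-third reduction, so p2 = 0.28 × 2/3 = 0.18667 (Appendix A); 1:1 allocation (Appendix A); power 90%; total 850, so 425 per arm; comparison of two proportions (Section 5.5).

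- Difference d = 0.09333, d² = 0.0087111
- Unpooled variance V1 = 0.28 × 0.72 + 0.18667 × 0.81333 = 0.35342, √V1 = 0.59449
- Pooled variance V0 = 2 × 0.23333 × 0.76667 = 0.35778, √V0 = 0.59815
- z for 90% power = 1.2816; z for 5% two-sided = 1.9600; z for 2.5% two-sided = 2.2414

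**Formulas (normal approximation, no continuity correction).**

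- Unpooled, per arm: n = (zα + zβ)² × V1 / d²
- Pooled, per arm: n = (zα√V0 + zβ√V1)² / d²
- Power at n per arm, pooled: Φ[(d√n − zα√V0) / √V1]; unpooled: Φ[d√n / √V1 − zα]

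**Step 1: the plan's figure at 5% two-sided.**

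- Unpooled: 10.507 × 0.35342 / 0.0087111 = 426.3 per arm, total 852.6
- Pooled: (1.1723 + 0.7619)² / 0.0087111 = 429.5 per arm, total 858.9
- Power at 850: pooled Φ[(1.9241 − 1.1723) / 0.59449] = Φ(1.265) = 89.7%; unpooled Φ(3.2366 − 1.9600) = 89.9%

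The stated 850 and 90% are reproduced.

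**Step 2: the same inputs at 2.5% two-sided.**

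- Unpooled: 12.411 × 0.35342 / 0.0087111 = 503.5 per arm, total 1,007.1
- Pooled: (1.3407 + 0.7619)² / 0.0087111 = 507.5 per arm, total 1,015.0
- Power at 850: pooled Φ[(1.9241 − 1.3407) / 0.59449] = Φ(0.981) = 83.7%; unpooled 84.0%

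A continuity correction moves both totals further up (902 at 5%, 1,058 at 2.5%), so it does not rescue the 2.5% reading.

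**Step 3: Table 2** (pooled, each arm rounded up; usual-care rates 28 / 30 / 32 / 35%).

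| Power, reduction | Printed | At 5% two-sided | At 2.5% two-sided |
|---|---|---|---|
| 80%, 30% | 810 / 740 / 680 / 600 | 806 / 734 / 674 / 594 | 976 / 890 / 816 / 720 |
| 80%, 33.3% | 640 / 590 / 540 / 480 | 644 / 588 / 538 / 476 | 780 / 712 / 652 / 576 |
| 90%, 30% | 1080 / 990 / 900 / 800 | 1078 / 982 / 900 / 794 | 1272 / 1160 / 1064 / 938 |
| 90%, 33.3% | 850 / 790 / 720 / 640 | 860 / 784 / 720 / 634 | 1016 / 928 / 850 / 750 |

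At 5% every cell is within 1.3% of the printed value. At 2.5% every cell is 17% to 22% larger.

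**Step 4: other power statements.**

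- Section 5.2, more than 80% power for a 30% reduction: at the 28% rate, 82.1% at 5% and 73.8% at 2.5%.
- Section 5.5.1, about 50% power for a 50% reduction in a 15% subgroup: taking 28% against 14%, 49.2% at 5% and 38.0% at 2.5%.

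Both statements fit 5% only.

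**Step 5: what the two thresholds would do.** Take 425 women per arm, 119 usual-care events (28%) and an uncorrected pooled z-test, ignoring interim looks.

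- 91 pessary events: z = 2.227, p = 0.026
- 94 pessary events: z = 1.979, p = 0.048

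From 91 to 94 events, the result meets 5% and misses 2.5%. With one O'Brien-Fleming-type look at 50%, the final critical values become 1.969 and 2.246, and the same two z values still fall between them.

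**The case against.** **The disputed lines are sample-size inputs.** Neither is worded as a decision rule. The only section that sets error control for testing the primary outcome is 5.4, and its one-sided .025 for benefit matches Section 5.2. On that view the operative rule can be read from the body, and Appendix A holds a summary-page slip with no effect on N, power or monitoring. This is a fair argument for calling the repair small. It does not remove the contradiction: Section 5.5 states no level, and no text ranks the body above the appendix.

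**850 does give 90% power at 2.5% two-sided if the usual-care rate is 32%.** This is true. For a 33.3% reduction at 2.5%, power at 850 is 87.1% at 30%, 90.0% at 32% and 93.5% at 35%. But Appendix A states 28%, and Table 2 prints 720 for 32%.

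**Section 5.4 is not a 5% two-sided rule.** This is correct. The lower boundary spends its own one-sided .05, so the two tails together allow up to 0.025 + 0.05 = 7.5%. Section 5.4 agrees with 5% two-sided on the benefit side only.

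**The event range depends on the test.** Section 5.5 does not name one. With Fisher's exact test the range moves to 90 to 93 events (p = 0.026 at 90, 0.057 at 94). A gap of the same width remains.

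**Conclusion.** The concern holds. Appendix A's 2.5% two-sided contradicts Section 5.2 and Table 2, and it is inconsistent with the rates, power and sample size listed beside it. Those figures reproduce at 5% two-sided (853 to 859 women; 89.7% to 89.9% power at 850) and not at 2.5% (1,007 to 1,015 women; about 84%).

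This is not a finding that the trial is underpowered. It shows that 850 follows from the plan's own inputs: 28%, a 33.3% reduction and 1:1 allocation. It does not test whether 28% is the right rate. The plan states no inflation of 850 for loss to follow-up, but excluding 2% of women would still leave 89.1% power, and one interim look as planned leaves 89.6%.

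That a one-sided level was labelled two-sided is an inference. The correction does not depend on it.

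**What to change.** In Appendix A, change the error-rate line to: *Type I error = 5% two-sided (2.5% one-sided for benefit)*. Leave 850, Section 5.2, Table 2 and Section 5.4 as they are. The sponsor should confirm that no stricter level was intended. If one was, about 1,007 to 1,015 women would be needed for 90% power at the stated rates.

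The cost is one line, with no extra women and no change to any other section. The correction should be made before outcome results by arm are known.
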